5.3 Treatment Plan

The treatment regimen and schedule are as follows:

Induction phase:

Agent	Dose	Route	Schedule
Ublituximab	900 mg	IV	Cycle 1 : Day 1, Day 8, and Day 15 Cycles 2-6 : Day 1
Acalabrutinib	100 mg - Twice daily	Orally	Every day of each cycle
Umbralisib	800 mg - Once daily	Orally	Cycle 1 : Days 1-14 Cycles 2-6 : Days 1-7

Maintenance phase:

Agent	Dose	Route	Schedule
Ublituximab	900 mg	IV	Every 2 cycles (Cycles 8, 10, 12, 14, 16, 18, 20, 22, 24) , on Day 1, starting on Day 1 of Cycle 8
Acalabrutinib	100 mg - Twice daily	Orally	Every day of each cycle
Umbralisib	800 mg - Once daily	Orally	Days 1-7 of each cycle

Treatment will be administered on an *out-patient* basis (in-patient administration is allowed if deemed necessary by the Investigator).

5.4 Agent Administration

5.4.1 Required Premedications

- Patients should be premedicated prior to all ublituximab infusions. Pre-medications should include an antihistamine (diphenhydramine 50 mg or equivalent), and a corticosteroid (dexamethasone 10-20 mg or equivalent).
 - If pre-medications are administered IV: start the ublituximab infusion 30 minutes after conclusion of the last pre-medication infusion
 - If pre-medications are administered orally: start the ublituximab infusion 45-60 minutes after ingestion of the oral pre-medications
 - Adjusting antihistamine and corticosteroid doses, adjusting the timing of administration and/or additional pre-medications may be used at investigator discretion for additional prophylaxis against infusion related reactions
 - Use of oral acetaminophen 650 mg (or equivalent) should be restricted to patients who experience fever or pyrexia during week 1 dosing, or as clinically warranted
- After cycle 6, if use of a corticosteroid is of clinical concern, please contact the Principal Investigator.
- Use of anti-pneumocystis and antiviral prophylaxis is required for subjects receiving umbralisib. Refer to [Section 5.10](#) for guidelines.
- Prophylaxis with an antiviral agent effective against hepatitis B is required in subjects with a prior known history of hepatitis B and for those with a positive anti-HBc with negative HBsAg at screening. Promptly consult clinicians with an expertise in managing subjects with a prior history of hepatitis B regarding monitoring and consideration of options for hepatitis B antiviral therapy for prophylaxis/ treatment.

5.4.2 Ublituximab

Ublituximab will be administered as an intravenous infusion through a dedicated line. **Do not** administer as an IV push or bolus. Do not mix ublituximab with, or administer as an infusion with, other medicinal products.

The first infusion of ublituximab (Cycle 1, Day 1) will be administered over a target period of 4 hours. Ublituximab infusions on Cycle 1, Days 8 and 15 will be administered over a target period of 3 hours. For all subsequent ublituximab infusions, infusion time may be reduced to approximately 90 minutes.

Since infusion-related hypotension may occur, consider holding antihypertensive medications 12 to 24 hours prior to and throughout infusion of ublituximab. Decision to withhold antihypertensive medication is at investigator discretion.

Medication and resuscitation equipment must be available per institutional guidelines prior to ublituximab administration for the emergency management of potential anaphylactic reactions.

5.4.3 Acalabrutinib

Acalabrutinib will be administered as a 100 mg tablet taken orally approximately every 12 hours. The tablets should be swallowed intact with water without being crushed, dissolved, broken, or chewed. Acalabrutinib can be taken with or without food.

If a dose is missed, it can be taken up to 3 hours after the scheduled time with a return to the normal schedule with the next dose. If it has been > 3 hours, the dose should not be taken and the participant should take the next dose at the scheduled time. The missed dose will not be made up and must be returned to the site at the next scheduled visit.

As acalabrutinib is metabolized by CYP3A, participants should be strongly cautioned against using herbal remedies or dietary supplements (in particular, St John's wort, which is a potent CYP3A inducer). Otherwise, subjects should maintain their regular diet unless modifications are required to manage an AE such as diarrhea, nausea, or vomiting.

5.4.4 Umbralisib

Umbralisib should be taken at approximately the same time each day within 30 minutes of starting a meal. Subjects should be instructed to swallow the tablets whole and should not chew or crush them.

If a dose of umbralisib is missed, it should be taken as soon as possible on the same day. If it is missed for a period of greater than 12 hours, it should not be replaced. If vomiting occurs, no attempt should be made to replace the vomited dose.

5.5 Assessments and Special Monitoring

For a detailed list of all study procedures including timing and windows, see [Section 10](#).

Note: Initiate a new cycle after all procedures/safety assessments have been completed.

5.5.1 Special Monitoring

- *Infusion reactions*
 - Infusion related reactions including severe reactions have been reported with ublituximab administration.
 - If such a reaction were to occur, it might manifest with fever, chills, rigors, headache, rash, pruritus, arthralgias, hypotension, hypertension, bronchospasm, or other allergic-like reactions.
 - Refer to [Section 5.10](#) for management guidelines.
- *Infections*

- Participants receiving umbralisib are at risk for infection, including pneumocystis, herpes, aspergillus, cytomegalovirus (CMV), and respiratory syncytial virus (RSV), as well as various bacterial infections. Use of anti-pneumocystis and antiviral prophylaxis is required for subjects receiving umbralisib.
- Participants receiving acalabrutinib are at risk for infection (bacterial, viral, or fungal).
- Refer to [Section 5.10](#) for guidelines.
- *Tumor lysis syndrome (TLS)*
 - A TLS laboratory assessment (serum chemistry) will be performed during cycle 1 (see [Section 10.0](#)).
 - Refer to [Section 5.10](#) for guidelines.
- *Hepatitis B reactivation*
 - In addition to mandatory prophylaxis with an antiviral agent effective against hepatitis B ([Section 5.4.1](#)), monitor subjects with a prior history of hepatitis B and those with a positive anti-HBc with negative HBsAg at screening closely as clinically indicated based on liver tests and any observed signs/symptoms such as jaundice, abdominal pain, dyspepsia, dark-colored urine often accompanied by lighter-than-normal colored stools, nausea, vomiting or fatigue.
 - Refer to [Section 5.10](#) for guidelines when there is an increase in liver enzymes while on study.

5.6 Duration of Therapy and Criteria for Removal from Protocol Therapy

Participants will receive protocol therapy until one of the below criteria are met:

- Confirmed Disease progression per 2014 Lugano classification
- Completed protocol therapy
- Participant is deemed intolerant to protocol therapy because of toxicity, despite dose modification/delay
 - **Note:** If one agent is discontinued due to toxicity, then the participant may continue to receive the other study agents
- General or specific changes in the patient's condition which render the patient unacceptable for further treatment in the judgment of the investigator
- Withdrawal of consent for further protocol therapy (See [Section 17.5](#))

Once participants meet criteria for removal from protocol therapy, the participant should then proceed to follow-up assessments ([Section 5.7](#)).

Documentation of the reason for discontinuing protocol therapy and the date effective should be made in the Electronic Health Record/medical record and appropriate eCRF.

The COH DCC and the Study PI should be promptly notified of the change in participant status.

5.7 Follow-Up

Following completion of protocol therapy, participants will enter follow-up.

Follow-up is comprised of:

- **Safety Follow-up**- 30 days post-last dose of protocol therapy.
 - **Note** the period for safety follow-up will be extended until stabilization or resolution for all reportable AEs (per the agreement of the Study PI) and accompanying follow-up safety report.
- **Response Follow-up**- for those who have yet to have disease progression and have not initiated a new anti-lymphoma therapy.

- **Survival Follow-up**- for all participants who have progressed OR completed Active Response Follow-Up OR initiated a new anti-lymphoma therapy. It will entail (a) Disease status (for those who have yet to progress) (b) Vital status (all participants).

Assessment time points and windows are detailed in [Section 10](#).

Note: if a participant continues therapy beyond 25 cycles with acalabrutinib for a total of 6 years of protocol therapy, the participant will only proceed with the safety follow-up visit; there will be no response/survival follow-up.

5.8 Duration of Study Participation

Study participation may conclude when any of the following occur:

- Completion of study activities (treatment and follow-up)
- Withdrawal of consent (See [Section 17.5](#))
- Patient decided to proceed with autologous transplantation
- Participant is lost to follow-up. All attempts to contact the participant must be documented.
- At the discretion of the investigator for safety, behavioral, study termination or administrative reasons

Documentation of the reason for discontinuing study participation and the date effective should be made in the Electronic Health Record/medical record and appropriate eCRF.

The COH DCC and the Study PI should be promptly notified of the change in participant status.

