Correlative tumor tissue ^v	X ⁿ										X ^o					
Bone marrow biopsy/ aspirate ^{p, v}	X										X					

- a. Screening activities to occur within 28 days prior to start of protocol therapy except for laboratory assessments.
- b. In the absence of treatment delay, each treatment cycle lasts 28 ± 3 days during Induction, and 28 ± 7 days during Maintenance.
- c. Maintenance phase for participants with stable disease or better response (PR or CR) at the end of Induction therapy.
- d. Activities to be performed within 72 hours prior to study drug administration.
- e. The Safety 30 days post-last dose assessments to occur 30 (± 7) days post-last dose or, if > 30 days elapsed since last dose, within 7 days after decision to end treatment. Expedited reporting will occur during this period. Safety follow-up may be extended until resolution/ stabilization of reportable AEs.
- f. For participants yet to progress, Active Follow-up will occur at 6, 12, 18 and 24 months (± 30 days for all) from last on-treatment scan until disease progression or the initiation of a new anti-lymphoma therapy.
- g. Participants who end Active Follow-up will enter Survival Follow-up. Survival assessment to occur bi-annually or as requested by the Study PI via medical record review, review of social security registry, or telephone call.
- h. *Standard physical exam* includes weight.
- i. *Vital signs*: heart rate, blood pressure, respiration rate, and temperature.
- j. *Women of childbearing potential*: Pregnancy serum test. For the screening time point, serum pregnancy test must be performed within 3 days prior to start of protocol therapy.
- k. *Screening laboratory assessments* to be performed within 14 days prior to start of protocol therapy.
- l. *Serum chemistry panel* to include: glucose, Blood Urea Nitrogen (BUN), creatinine, uric acid, total protein, albumin, magnesium, bicarbonate, calcium, inorganic phosphorous, sodium, potassium, chloride, total bilirubin, alkaline phosphatase, ALT, AST, and LDH.
- m. Correlative blood will also be collected at time of relapse. Refer to [Section 9.1.3](#) for additional information.

- n. Archival tumor tissue to be submitted post-enrollment when available. Refer to [Section 9.1.1](#).
- o. If safe and feasible, submission of left-over tissue from a standard of care tumor biopsy (fresh core or excisional biopsy) for participants who progress/relapse during study is encouraged. Refer to [Section 9.1.1](#).

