11.3 Secondary Endpoint(s)

Overall response rate (ORR): defined as the proportion of response-evaluable participants (see [Section 12.2](#)) that achieve a best response of either CR or PR during protocol therapy.

Progression-Free Survival (PFS): defined as the duration of time from start of protocol treatment to time of disease relapse/progression, start of non-protocol anti-lymphoma therapy, or death due to any cause, whichever occurs earlier. For patients who are alive and have not had disease relapse/progression at the last follow-up, it is censored at the time of last follow-up. .

Overall Survival (OS): defined as the duration of time from start of protocol treatment to time of death due to any cause. For patients who are alive at last follow-up, it will be censored at the time of last follow-up.

Duration of Response (DOR): Defined as the time from the first achievement of PR or CR to time of PD, start of non-protocol anti-lymphoma therapy, or death, whichever earlier. Patients who never achieve PR or CR during protocol therapy are excluded. Patient who has not had any of the failure events above at last follow-up is censored at the time of last follow-up.

Toxicity: Toxicity and adverse events will be recorded using the NCI CTCAE 5.0 scale. Observed toxicities will be summarized by type (organ affected or laboratory determination such as absolute neutrophil count), severity (by NCI CTCAE v5.0 and nadir or maximum values for lab measures), date of onset, duration, reversibility, and attribution.

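### Section 5.8 lets follow-up end when a patient decides on autologous transplant, in conflict with the survival follow-up rule in 5.7 and the PFS/DOR event definition in 11.3

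*Combined protocol and SAP*

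**What the plan says.** Section 5.8 opens with "Study participation may conclude when any of the following occur" and includes "Patient decided to proceed with autologous transplantation" in the list. Its first item is completion of study activities, which it spells out as treatment and follow-up. Participation in 5.8 therefore covers follow-up as well as protocol therapy.

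Three other places describe what happens after therapy:

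- Section 5.6: "Once participants meet criteria for removal from protocol therapy, the participant should then proceed to follow-up assessments".
- Section 5.7: Survival Follow-up is "for all participants who have progressed OR completed Active Response Follow-Up OR initiated a new anti-lymphoma therapy", with vital status collected for all of them and disease status for those not yet progressed. The one exception written into 5.7 is for participants who reach six years of protocol therapy on continued acalabrutinib.
- Section 10.0, Study Calendar, footnote g: "Participants who end Active Follow-up will enter Survival Follow-up".

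None of the three exempts transplant.

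Section 11.3 ends PFS at the earliest of relapse or progression, "start of non-protocol anti-lymphoma therapy, or death due to any cause, whichever occurs earlier". DOR also treats the start of non-protocol therapy as a failure. The PFS censoring sentence reads "For patients who are alive and have not had disease relapse/progression at the last follow-up, it is censored at the time of last follow-up"; for OS it is "For patients who are alive at last follow-up, it will be censored at the time of last follow-up". Section 12.5 estimates PFS and OS by Kaplan-Meier and states no sensitivity analysis for patients who leave the study.

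**The concern.** The trigger in 5.8 is the patient's decision, which comes before any transplant or conditioning has begun. Under 5.7 a progression-free patient at that moment belongs in Response Follow-up, and moves to Survival Follow-up once the new therapy starts. Under 5.8 the same patient may leave the study altogether. The protocol does not say which section prevails, so four sites could handle identical patients differently.

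Two things are at stake if the exit is used. First, OS is censored at the exit although the patient has not withdrawn consent to be followed. Second, if the patient has not progressed and the start date is never collected, an outcome that 11.3 defines as a PFS and DOR event enters the analysis as a censored observation. Kaplan-Meier assumes that censored patients have the same outlook as those who stay. A patient who leaves for a transplant may well not, so the assumption is hard to defend here, although that is an inference and the documents do not show it.

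**Working it through.** **No plan figure is at issue.** The plan states no power or precision for PFS, DOR or OS. Its design figures belong to the CR endpoint, and they reproduce: with 2 or fewer CRs in 9 as the stopping rule and 10 or more in 24 as success, the chance of early stopping at a 25% CR rate is 0.6007 (stated 60%), the type I error is 0.0485 (stated 0.05) and the power at 50% is 0.8055 (stated 0.8). Nothing below changes them.

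**The sections side by side, for a progression-free patient who decides on transplant**

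| Step | 5.6, 5.7 and footnote g | 5.8 exit used |
|---|---|---|
| Decision | Stays in follow-up | Participation may end |
| Transplant or conditioning starts | PFS/DOR event under 11.3; moves to Survival Follow-up | Event only if the start date is captured anyway; otherwise censored |
| Afterwards | Vital status collected | OS censored at last follow-up |

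The documents do not say in so many words that autologous transplant is non-protocol anti-lymphoma therapy. It is not part of protocol therapy, so that is the plain reading. The PFS censoring sentence adds to the difficulty: it mentions only relapse or progression, so a patient who starts new therapy without progressing fits both the event rule and the censoring rule.

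**Size for PFS (illustration).** Inputs: N = 24 evaluable patients (section 12.1). Assumed: k progression-free patients leave for transplant before any other event, m other events follow, and nobody else is censored before the last of these.

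- Counted as events: S = (24 − k − m)/24.
- Censored: S = (24 − k − m)/(24 − k).

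| m | k | Event | Censored | Rise (points) |
|---|---|---|---|---|
| 4 | 1 | 19/24 = 79.2% | 19/23 = 82.6% | 3.4 |
| 4 | 2 | 18/24 = 75.0% | 18/22 = 81.8% | 6.8 |
| 4 | 4 | 16/24 = 66.7% | 16/20 = 80.0% | 13.3 |
| 8 | 1 | 15/24 = 62.5% | 15/23 = 65.2% | 2.7 |
| 8 | 2 | 14/24 = 58.3% | 14/22 = 63.6% | 5.3 |
| 8 | 4 | 12/24 = 50.0% | 12/20 = 60.0% | 10.0 |

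The censored value has the same numerator over a smaller denominator, so under these assumptions the error is always upward.

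**Size for OS (bounds).** Assume d = 3 deaths among the other patients.

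- k = 2 lost early: the estimate is 19/22 = 86.4%. With full follow-up it would lie between 19/24 = 79.2% (both dead) and 21/24 = 87.5% (both alive).
- k = 4 lost early: 17/20 = 85.0%, against 17/24 = 70.8% to 21/24 = 87.5%.

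The estimate falls inside the range each time, so the direction of the OS bias cannot be stated.

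**The case against.** The case against giving this much weight has several parts, and most of them stand as limits.

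- **The exit is permitted, not required.** Section 5.8 says participation may conclude. A reader might infer that every patient who chooses transplant is censored for PFS and DOR and lost for OS. The documents do not support that. Such a patient can be handled under 5.6 as withdrawing from further therapy and sent on to follow-up. Section 17.5 keeps survival follow-up for patients who withdraw only from treatment or from active procedures. Footnote g allows survival status to come from medical records, a registry or a telephone call. What remains is that 5.8 allows the opposite and no rule decides between them.
- **Timing matters.** If the transplant follows documented progression, the PFS and DOR event has already occurred and only OS is affected. Section 5.8 also requires the exit reason and its effective date to be recorded. That is not the start of transplant therapy, but a site that captures the start date as well can code PFS and DOR correctly.
- **The number of cases is unknown.** Exclusion 5 bars patients being debulked before a planned transplant, which points to few cases. The other entry routes still admit patients who could later be transplanted: age 65 or over without any transplant-ineligibility requirement, age 50 or over and unwilling to have intensive therapy, and age 18 or over with TP53 aberration or complex karyotype.
- **Informative censoring is not demonstrated.** A reader might infer that patients who leave are selected for fitness and response. That is plausible, but the documents describe no selection pattern.
- **The endpoints are secondary.** No test or decision rule depends on PFS, DOR or OS. A CR reached earlier in induction is carried forward when the end-of-induction assessment is missing (section 11.2), so the primary endpoint is largely protected.

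None of this removes the contradiction between 5.8 and 5.7.

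**Conclusion.** The point holds as a conflict in the text with a conditional effect on secondary endpoints. Section 5.8 permits an exit that 5.7 and footnote g do not allow for, and using it can turn an event defined in 11.3 into a censored observation.

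The PFS effect rests on three conditions: the site uses the exit, the patient has not progressed, and the transplant start date is not captured. Under the assumptions shown, it is 2.7 to 3.4 points for one patient and 10.0 to 13.3 points for four. The range of one to four patients is an assumption with no basis in the documents, so it should not be read as a forecast that 1/24 to 4/24 (4% to 17%) of the sample will be miscoded. DOR is open to the same miscoding. OS loses follow-up with unknown direction of bias; a claim that it is inflated would go too far. The CR endpoint and the two-stage design are not in question.

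The text should be corrected, because the inconsistency is plain, the PFS error can only flatter the regimen, and survival data left uncollected may not be recoverable later.

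**What to change.** Reconcile 5.8 with 5.7 and footnote g so that a decision to have an autologous transplant does not by itself end study participation or vital-status follow-up. Record the start date of transplant or conditioning in the eCRF as the date of non-protocol anti-lymphoma therapy for PFS and DOR. In the same edit, make the PFS censoring sentence in 11.3 match its event list by adding that no non-protocol anti-lymphoma therapy has started.

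These changes concern follow-up and data collection only. They propose no rule on who may have a transplant or when protocol treatment should stop.

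The cost is a short text edit, one date field if it is not already captured, and a few vital-status contacts that 5.7 already requires. Sample size, error rates and the stopping rule do not change.

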5.9 Prohibited and Concomitant Therapies/Medications

5.9.1 Allowed concomitant medications

If concomitant therapy must be added or changed, including over-the-counter medications or alternative therapies, the reason and name of the agent/therapy should be recorded in the eCRF and documented in the Electronic Health Record/medical record.

Concurrent glucocorticoid therapy as long as started for at least 7 days prior to study entry (<20 mg per day of prednisone or equivalent) is allowed as clinically warranted.

Vaccination Guidance: Based on nonclinical data, no changes are recommended to standard of care practices with regard to vaccinations in subjects treated with acalabrutinib. As appropriate, vaccines consistent with standard practices for specific subject populations should be used.

5.9.2 Precautionary and Prohibited medications/therapies

This is not intended to be an exhaustive list; the investigator should consider each concomitant medication and potential for drug-drug interactions.

- Prohibited from **Day 1 of protocol therapy until end of protocol therapy** (last day of study agent or decision to end study agent(s) whichever occurs later).
 - Herbal and natural remedies
 - Other investigational therapy
 - Other concurrent systemic anti-cancer therapy: chemotherapy, biological response modifiers, hormone therapy, surgery, palliative radiation therapy, or immunotherapy.
 - Live vaccines.
 - Systemic corticosteroid therapy at a daily dose ≥ 20 mg prednisone or equivalent. Patients may be using topical or inhaled corticosteroids.

- **Guidelines for co-administration with acalabrutinib:**

- Warfarin or equivalent Vitamin K antagonists are prohibited in patients on acalabrutinib as they may increase the risk of hemorrhage.
- Co-administration of acalabrutinib and a proton pump inhibitor should be avoided.
- Co-administration of acalabrutinib with a strong or moderate CYP3A inhibitor may increase acalabrutinib plasma concentrations resulting in increased toxicity. Use of strong or moderate CYP3A inhibitors should be avoided.
- Conversely, co-administration of acalabrutinib with a strong CYP3A inducer should be avoided as this may decrease acalabrutinib concentrations.

Refer to [Appendix E](#) for examples.

Refer to [Section 8.2.6](#) for appropriate acalabrutinib dose adjustments if co-administration with a CYP3A inhibitor or inducer is required.

If treatment with a gastric reducing agent is required, consider using a H2-receptor antagonist (e.g. famotidine) or an antacid (e.g. calcium carbonate).

- If receiving antacids, acalabrutinib dosing should be separated by at least 2 hours.
- If receiving H2-Receptor Antagonists, acalabrutinib should be taken 2 hours before taking a H2-receptor antagonist.

